### 8.1.2 Imputation of Partial Dates

Imputed dates will not be used to derive study day, duration (eg, duration of adverse events), or elapsed time variables.

Partial date imputation will follow Analysis Data Model (ADaM) conventions. The AdaM approach is to populate the numeric date variables with the imputed date and add a flag variable to the dataset that indicates the level of imputation.

The flag variable can contain the values: blank, 'D', 'M', 'Y'.

blank	indicates that no imputation was done
D = 'Day'	indicates that the day portion of the date is imputed
M = 'Month'	indicates that the month and day portions of the date are imputed
Y = 'Year'	indicates that the entire date (year, month, and day) is imputed

### Adverse Events

Imputations in the adverse events dataset are used for slotting events to the appropriate study time periods and for sorting in data listings. They will not be used to calculate duration of AEs. If an AE start or end date is missing, then the duration of the AE will be set to missing.

As a rule, the missing start date elements will be imputed with following priorities:

1. The event is counted as TEAE for IgPro20 with the earliest onset possible.
2. The event is counted as TEAE for Placebo with the earliest onset possible.

In Sequence B, if due to missing elements the event qualifies to either IgPro20 or Placebo, the event is assigned to be treatment-emergent in the IgPro20 period.

If the AE with missing start date elements is related to oral corticosteroid treatment the imputed start date must not be before the start date of the oral corticosteroid treatment.

Date	Missing Element	Rule
Start Date	day, month, and year	
Do not impute completely missing AE start dates.
 
Sequence A
 
 
• The AE will be deemed treatment-emergent in Study Period 1 (Week 1-25) if the AE end date does not indicate that the AE ended prior to IMP start date (week 1),
 
• otherwise the AE will be deemed not treatment-emergent.
 
 
Sequence B
 
 
• The AE will be deemed treatment-emergent in Study Period 2 (Week 25-53) if the AE end date does not indicate that the AE ended prior to IMP start date (week 25),
 
• else the AE will be deemed treatment-emergent in Study Period 1 (Week 1-25) if the AE end date does not indicate that the AE ended prior to IMP start date (week 1),
 
• otherwise the AE will be deemed not treatment-emergent.
 

Start Date	day, month only	
Sequence A
 
 
• If the year of AE start date is the same as the year of IMP start date (week 1), and the AE end date indicates the AE ended after IMP start date (week 1), then set AE start date to IMP start date (week 1),
 
• otherwise set AE month and day to January 1st
 
 
Sequence B
 
 
• If the year of AE start date is the same as the year of IMP start date (week 25), and the AE end date indicates the AE ended after IMP start date (week 25), and IMP start date (week 25) is not missing then set AE start date to IMP start date (week 25),
 
• else if the year of AE start date is the same as the year of IMP start date (week 1), and the AE end date indicates the AE ended after IMP start date (week 1) then set AE start date to IMP start date (week 1),
 
• otherwise set AE month and day to January 1st
 
 
Oral corticosteroid treatment
 
If the AE is related to oral corticosteroid treatment take the later date of first oral corticosteroid treatment start date and the date imputed to the rules in “Sequence A” or “Sequence B” above.

	day only	
Sequence A
 
 
• If the month/year of AE start date is the same as the month/year of IMP start date (week 1), and the AE end date indicates the AE ended after IMP start date (week 1) then set AE start date to IMP start date (week 1),
 

Date	Missing Element	Rule
		
 
otherwise set day of AE start date to 1
 
 
Sequence B
 
 
If the month/year of AE start date is the same as the month/year of IMP start date (week 25), and the AE end date indicates the AE ended after IMP start date (week 25), and IMP start date (week 25) is not missing then set AE start date to IMP start date (week 25),
 
else if the month/year of AE start date is the same as the month/year of IMP start date (week 1), and the AE end date indicates the AE ended after IMP start date (week 1) then set AE start date to IMP start date (week 1),
 
otherwise set day of AE start date to 1
 
 
Oral corticosteroid treatment
 
If the AE is related to oral corticosteroid treatment take the later date of first oral corticosteroid treatment start date and the date imputed to the rules in “Sequence A” or “Sequence B” above.

End Date	any date element	No imputation for completely or partially missing AE end dates; as applicable, report the AE as ongoing and the AE duration as missing.

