#### *Safety Analysis Set Extended – SAF-Ex*

The SAF-Ex analysis set comprises all subjects in the SAF who complete the first 24 weeks of double-blind treatment (Study Period 1) and receive any amount of the IMP between Week 25 and Week 53 (Study Period 2). The SAF-Ex analysis will be based on the actual treatment sequence received.

*Safety Analysis Set IgPro20 – SAF-IgPro20*

The SAF-IgPro20 analysis set comprises all subjects in the SAF who are randomized to Sequence A, and all subjects in SAF-Ex who are randomized to Sequence B.

*Pharmacokinetic Analysis Set - PK*

The PK analysis set comprises all subjects, without any protocol violations that may impact PK analysis, who provide rich PK samples (Week 37) for non-compartmental PK parameter estimation. Protocol violations that may impact PK analysis will be defined in detail in the BDRM before database lock.

*Safety Analysis Set for Study Period 3 – SAF-P3*

The SAF-P3 Analysis Set comprises all subjects in the SAF-Ex who completed the first 52 weeks of treatment in Study Period 1 and Study Period 2 and received any amount of the IMP after Week 52 (ie, in Study Period 3).

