## 11 Safety Analyses

All Safety analyses will be performed for the following periods and analysis sets:

- Week 1-EOP1 by treatment sequence (SAF)
- Week 25-EOP2 by treatment sequence (SAF-Ex)
- Week 53-EOP3 by treatment sequence (SAF-P3)

Additionally, adverse events will be presented using the following periods and analysis sets:

- IgPro20 Periods (SAF-IgPro20)  
Note: This is restricted to IgPro20 treatment

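### SAP 8.1.2: the Sequence B rule for an AE with no start date does not require a Week 25 infusion, so, read literally, undated AEs of placebo subjects who stopped in Period 1 fall outside every period table

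*SAP*

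**What the plan says.** SAP 8.1.2 (Adverse Events) sets two priorities for missing start-date elements. An event counts first under IgPro20; failing that, "The event is counted as TEAE for Placebo with the earliest onset possible". For Sequence B it adds: "In Sequence B, if due to missing elements the event qualifies to either IgPro20 or Placebo, the event is assigned to be treatment-emergent" (meaning under IgPro20).

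The rule for a completely missing start date in Sequence B then has three branches:

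1. Period 2: "The AE will be deemed treatment-emergent in Study Period 2 (Week 25-53) if the AE end date does not indicate that the AE ended prior" (the reference is the Week 25 IMP start).
2. Period 1: "else the AE will be deemed treatment-emergent in Study Period 1 (Week 1-25) if the AE end date does not indicate" an end before the Week 1 IMP start.
3. Otherwise the event is not treatment-emergent.

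The two Sequence B rules for partial dates (day and month missing; day missing) carry an extra condition on the Week 25 branch: "and IMP start date (week 25) is not missing then set AE start date to IMP start date (week 25").

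End dates are left alone: "No imputation for completely or partially missing AE end dates; as applicable, report the AE as ongoing and the AE duration as missing".

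On the reporting side, SAP 11 plans the Period 1 safety tables as "Week 1-EOP1 by treatment sequence (SAF"), the Period 2 tables on SAF-Ex, the Period 3 tables on SAF-P3, and an additional AE presentation for IgPro20 periods on SAF-IgPro20. SAP 6 restricts SAF-Ex to "all subjects in the SAF who complete the first 24 weeks of double-blind treatment (Study Period 1) and receive any amount of the IMP between" (the interval meant is Study Period 2).

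**The concern.** The partial-date rows show that the authors foresaw Sequence B subjects with no Week 25 infusion, and the protocol provides for stopping IMP during Period 1 (section 4.3.1). The row for a completely missing start date lacks the same protection. For such a subject there is no Week 25 infusion that the end date could precede, so on a literal reading the first branch is met and the Period 1 branch is never reached. The event is labelled as emerging under IgPro20, which the subject never received.

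What is at stake is the even-handedness of the randomised AE comparison in Week 1-EOP1. The same undated AE in a Sequence A subject who stopped early stays in Period 1, unless it ended before Week 1. On the placebo side the event would leave the numerator of the annualised TEAE rate (SAP 11.2), while the subject's Period 1 observation time stays in the denominator.

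**Working it through.** The plan states no figure on this point, so there is none to reproduce. The check has two parts: follow the rule through the analysis sets, then size the effect under stated assumptions.

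**Which tables can hold the event.** Take a Sequence B subject who stopped IMP in Period 1.

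- SAF: yes (randomised and received IMP). Its period table is Week 1-EOP1 and counts events with onset in Period 1 (SAP 8.3.1, 11).
- SAF-Ex: no (24 weeks not completed, no IMP from Week 25).
- SAF-IgPro20: no (Sequence B members come only from SAF-Ex).
- SAF-P3: no (a subset of SAF-Ex).

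So the only period table open to this subject is Week 1-EOP1, and only if the event is assigned to Period 1.

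**Where the rule sends the event.** A comparison with a Week 25 date that does not exist is taken as not showing an earlier end.

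| AE end date | Row as written | Period tables | With the non-missing condition |
|---|---|---|---|
| Missing or ongoing | Period 2 | none | Period 1, Week 1-EOP1 (placebo) |
| Before Week 1 | Period 2 | none | Not treatment-emergent |
| Within Period 1 | Period 2 | none | Period 1, Week 1-EOP1 (placebo) |
| After the Week 25 time point | Period 2 | none | Period 1, Week 1-EOP1 (placebo) |

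As written, 4 of 4 cases appear in no period table. With the condition, 3 go to the placebo table and 1 is correctly not treatment-emergent. For subjects who did receive the Week 25 infusion, the assignment is the same with and without the condition in all four cases.

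The second and third rows depend on the comparison convention. If a programmer substituted the planned Week 25 date, those two events would be assigned correctly, but the missing or ongoing case and the late-ending case would still go to Period 2.

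**Size.** The only documented input is 63 subjects planned per sequence (SAP 4.5). The rest are assumptions: 5% to 20% of Sequence B stop in Period 1, each with 4 AEs, and 0.5% to 2% of AEs have no start date at all.

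- Subjects: 63 × 0.05 = 3.15, about 3; 63 × 0.20 = 12.6, about 13.
- Low end: 3 × 4 × 0.005 = 0.06 events.
- High end: 13 × 4 × 0.02 = 1.04 events.

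**The case against.** The strongest reply is that the section already answers the question. Its general rule gives IgPro20 precedence only where an event could belong to either treatment. An event in a subject who never received IgPro20 cannot, and Table 8 starts Period 2 at a Week 25 infusion that did not occur. A programmer guided by that rule would count the event under placebo. SAP 8.2 also refers to separate dataset specifications, which may contain the check and are not available here. This stands in part: the literal result is one of two readings. It does not remove the point, because the row and the general rule give different answers and the two neighbouring rows show the wording that would settle it.

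Three stronger readings are tempting, and the documents do not support them.

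- *The events disappear from reporting.* They do not. SAP 11.2 plans an overall TEAE analysis besides the period analyses, lists all AEs whenever reported, and lists all serious TEAEs. The gap concerns the period and IgPro20 tables. Table 8 also defines a combined Week 1-EOP2 safety period, but SAP 11 assigns it no table or analysis set.
- *Every undated AE of such a subject is certain to be misplaced.* That holds only on the literal reading and, for events that ended early, only under one treatment of a missing comparison date.
- *The rule protects IgPro20.* The direction is the opposite. Losing placebo events from Week 1-EOP1 lowers the placebo count and makes IgPro20 look relatively worse. It cannot conceal an IgPro20 signal, since the affected subjects received only placebo.

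It is also fair to say that the trigger should be rare. AEs are documented at visits, data are queried and cleaned before unblinding, and serious events must be reported within 24 hours of awareness (protocol 8.5, 13.5.2, 6.3.3, 9.6.3).

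**Conclusion.** The point holds as a defect in one row of the imputation table. For a completely missing start date in Sequence B, SAP 8.1.2 does not require that the Week 25 infusion took place. Taken literally, it assigns undated AEs of placebo subjects who stopped in Period 1 to a period in which no analysis set contains them, against the general rule of the same section.

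The consequence is minor. The 0.06 to 1.04 events rest wholly on assumed stop rates, AE counts and undated fractions, and on the literal reading. The distortion is one-sided, against IgPro20. Efficacy, multiplicity and the detection of IgPro20 harm are not affected. It is worth correcting because the plan now supports two answers for a safety table.

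**What to change.** In the first Sequence B branch of the row for a completely missing start date, add the condition that the Week 25 IMP start date is not missing, joined by *and* to the existing end-date test, as the two partial-date rows already do. The existing second branch then assigns these AEs to Study Period 1 under placebo, and the third marks those that ended before Week 1 as not treatment-emergent.

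The cost is one clause in the SAP and one condition in the program, with a matching check of the dataset specifications. Results for subjects who received the Week 25 infusion do not change. The change should be made before unblinding for the EOP1 analysis, which is when SAP 3 requires decisions on the primary data analysis to be settled.

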### 8.3.1 Study Time Periods for Adverse Events

Adverse events (AEs) with onset date/ time after start of first infusion of IMP are TEAEs. Assessment whether an AE is considered treatment-emergent, will take place after imputation of partially missing dates (see Section 8.1.2).

The TEAE analysis will be done for the periods and groups shown in Section 11. An AE will be counted for the analysis of a period if the onset of the event falls within the period. For the definition of start and end of the periods see [Table 8](#) and [Table 9](#).

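### Read literally, SAP 8.1.2 dates an ongoing AE with a partial start date in an infusion month or year before that infusion, so it is lost as a TEAE or, in Sequence B, counted under placebo, against the SAP's own priority

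*SAP*

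**What the plan says.** The Adverse Events part of SAP 8.1.2 opens with two priorities for missing start-date elements. The first is "The event is counted as TEAE for IgPro20 with the earliest onset possible"; the second is "The event is counted as TEAE for Placebo with the earliest onset possible". For Sequence B, when an event could belong to either period, "the event is assigned to be treatment-emergent in the IgPro20 period".

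The table that follows applies two different end-date tests.

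- **Start date completely missing.** The test is negative: the AE is treatment-emergent "if the AE end date does not indicate that the AE ended prior to IMP start date (week 1"), with a parallel clause for Week 25 in Sequence B.
- **Day missing, or day and month missing.** The test is positive. If the known year (or month and year) matches the infusion and "the AE end date indicates the AE ended after IMP start date (week 1), then set AE start date to IMP start date". The Sequence B clause for the switch likewise requires a match "and the AE end date indicates the AE ended after IMP start date (week 25"). If the test fails, onset becomes day 1 of the month or 1 January.

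For end dates the table says "No imputation for completely or partially missing AE end dates; as applicable, report the AE as ongoing". SAP 8.3.1 decides treatment-emergent status after imputation and assigns the period by onset. It also says that AEs "with onset date/ time after start of first infusion of IMP are TEAEs"; SAP 11.2 agrees, whereas Protocol 10.4.3 includes AEs reported at the start of treatment as well as after it.

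**The concern.** An ongoing AE has not ended and has no end date, so nothing shows that it ended after the infusion. It passes the negative test and fails the positive one. An ongoing AE with no start date at all is therefore treatment-emergent, while one with a known month or year may not be. Less information gives the more conservative answer, the reverse of what the opening priorities intend.

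The records at risk are unresolved events that began around the first infusion or the switch to IgPro20. Open AEs are to be expected: the EOP1 analysis takes AEs from all subjects treated in any period at the data cut-off (SAP 3 and 4.6.1). At stake are the TEAE counts and annualized rates, above all in the tables for IgPro20 exposure.

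**Working it through.** The plan gives no figure to reproduce. The check applies the written rules to dated examples and then sizes the effect under stated assumptions.

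**Step 1: examples.** Week 25 is Week 1 plus 168 days (24 weeks). The last column gives the result for the same AE with an end date of 1 December 2022, or for the ongoing AE under the negative test; the two agree in every row. Dates imputed to the infusion day are counted as on treatment, as Protocol 10.4.3 allows.

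| Seq. | Week 1 | Week 25 | Recorded onset | Ongoing AE, rule as written | Resolved AE, or negative test |
|---|---|---|---|---|---|
| A | 15 Mar 2021 | 30 Aug 2021 | Mar 2021 | 1 Mar 2021, not a TEAE | 15 Mar 2021, IgPro20 |
| A | 15 Mar 2021 | 30 Aug 2021 | 2021 | 1 Jan 2021, not a TEAE | 15 Mar 2021, IgPro20 |
| A | 15 Mar 2021 | 30 Aug 2021 | Apr 2021 | 1 Apr 2021, IgPro20 | 1 Apr 2021, IgPro20 |
| B | 15 Mar 2021 | 30 Aug 2021 | Mar 2021 | 1 Mar 2021, not a TEAE | 15 Mar 2021, placebo |
| B | 15 Mar 2021 | 30 Aug 2021 | Aug 2021 | 1 Aug 2021, placebo | 30 Aug 2021, IgPro20 |
| B | 15 Mar 2021 | 30 Aug 2021 | 2021 | 1 Jan 2021, not a TEAE | 30 Aug 2021, IgPro20 |
| B | 15 Sep 2021 | 2 Mar 2022 | 2022 | 1 Jan 2022, placebo | 2 Mar 2022, IgPro20 |
| B | 15 Mar 2021 | 30 Aug 2021 | Sep 2021 | 1 Sep 2021, IgPro20 | 1 Sep 2021, IgPro20 |

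Only the missing end date drives the changes. Onsets in a month that contains no infusion are handled correctly.

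**Step 2: share of ongoing AEs with a partial start date.** Assume the first infusion falls equally often on each of 365 days, and true onset is uniform over 364 days (24 + 28 weeks). That gives 365 × 364 = 132,860 pairs.

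*Sequence A, day and month missing.* An infusion on day i of the year (i = 2 to 365) leaves 366 − i onset days in that year. The sum is 364 × 365 / 2 = 66,430, and 66,430 / 132,860 = 50.0% become non-treatment-emergent.

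*Sequence A, day missing.* A month of L days contributes L(L − 1)/2 pairs. The year gives 7 × 465 + 4 × 435 + 378 = 5,373, and 5,373 / 132,860 = 4.0% become non-treatment-emergent.

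*Sequence B, by enumeration of the same pairs, as a share of all on-treatment AEs of this kind:*

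| Change of class | Day missing | Day and month missing |
|---|---|---|
| IgPro20 to placebo | 4.0% | 24.8% |
| IgPro20 to not a TEAE | 0% | 14.5% |
| Placebo to not a TEAE | 4.0% | 35.5% |

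As a check, the last two rows sum to 4.0% and 50.0%, matching Sequence A.

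**Step 3: negative test throughout.** No on-treatment ongoing AE is lost, and none moves from IgPro20 to placebo. In Sequence B, 4.0% (day missing) and 35.5% (day and month missing) move from placebo to IgPro20, as the stated tie-break intends.

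**The case against.** The best defence is that the intent is explicit. The two priorities and the Sequence B tie-break come first, SAP 8.2 defers full derivations to separate dataset specifications, and a programmer guided by the priorities could treat ongoing as meeting the test. The case also needs a partial onset date in a narrow window and no end date. AEs are documented at the Week 1 and Week 25 visits, questionable data are queried, and all AEs are listed regardless. This bears on size, and it stands there. It does not remove the contradiction: no sentence says that an ongoing AE counts as having ended later, and specifications outside the documents cannot be assumed to correct the rule.

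Three stronger readings are tempting and are not supported.

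- *The rule favours IgPro20 in the placebo-controlled comparison.* Read literally, an ongoing AE takes the same fallback date in both sequences. In the Week 1 month it is lost in both. In the Week 25 month it is dated to day 1 and falls in Study Period 1 in both.
- *Every AE without a complete end date is misclassified.* A partial end date that clearly falls after the infusion meets the test. An infusion on day 1 of the known month, or on 1 January when only the year is known, causes no loss at Week 1. For corticosteroid-related AEs the later steroid start date applies, which brings some back on treatment.
- *Any Sequence B AE known only to the year of the switch becomes a placebo event.* That holds when Week 1 fell in the previous year. If both infusions fall in the same year, the AE becomes non-treatment-emergent, unless Week 1 was on 1 January.

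**Conclusion.** The point holds for ongoing AEs with no end date and a start date missing the day, or the day and month, where the known month or year contains an infusion that is not on its first day. Around Week 1 such an AE is lost as a TEAE in either sequence. Around Week 25, a Sequence B AE known to the month is counted under placebo; one known only to the year goes to placebo or is lost, depending on the year of Week 1.

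The consequences are lost TEAEs in both arms and under-counting in the IgPro20-period tables (SAF-Ex for Week 25 to EOP2, and SAF-IgPro20). Arm-specific bias in Week 1 to EOP1 is not shown. The percentages rest on uniform dates and describe only this class of record. The documents do not say how many there are, so the effect on the tables cannot be sized; it is probably small. The after versus at-or-after difference in the TEAE definition is a companion point with no misclassification demonstrated, but it matters once dates are imputed to the infusion day.

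**What to change.** In the two partial-date rows of SAP 8.1.2, replace the positive end-date test in all six conditions (one for Sequence A and two for Sequence B in each row) by the negative test of the completely-missing row, so that ongoing AEs qualify. Keep the requirement that the Week 25 date is not missing. In SAP 8.3.1 and 11.2, define a TEAE as onset at or after the start of the first infusion, in line with Protocol 10.4.3, so that an AE imputed to the infusion day counts.

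The cost is wording and minor programming. A few more events may count under IgPro20, including some Sequence B events that truly began on placebo. Sequence A has no Week 25 clause, so its AEs from that month stay in Study Period 1. That asymmetry comes from the SAP's own tie-break and works against the product.

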## Medical History

Date	Missing Element	Rule
Start Date	any date element	No imputation for completely or partially missing start dates
End Date	day, month, and year	Do not impute completely missing Medical History end dates. The Medical History will be deemed “Concomitant medical condition”.
	day, month only	Set the end date to December 31 st .
	day only	Set the end date to the last day of the month.

